13.2.1.2. EXACT-Defined Recovery for CAT Trigger

If the study day following EXACT-defined recovery for a participant occurs within a scheduled assessment window, an additional analysis time-point will be programmatically created for that scheduled visit. For example, if EXACT-defined recovery occurred on Day 56, then a Day 56 Visit will be programmatically created with the data from the Recovery visit so that it can be summarised/analysed in both the Visit and Recovery categories.

Due to software limitations of the electronic PRO device, the study day following EXACT-defined recovery from the index exacerbation is not derived according to the EXACT User Manual. Instead, it has been derived using a 3-day Rolling Average that is calculated as the mean EXACT score [Day X-2, Day X-1, Day X].

13.3. Appendix 3: Study Phases and Treatment Emergent Adverse Events

13.3.1. Study Periods

13.3.1.1. 12-Week Treatment Period

The 12-Week Treatment Period is assigned from Study Day 1 to Study Day 84.

13.3.1.2. 12-Week Follow-Up Period

The 12-Week Follow-up Period is assigned from Study Day 85 to Study Day 168.

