7.2. Secondary Efficacy Analyses

7.2.1. Rate of exacerbations

Rate of exacerbation is defined as the frequency of exacerbations (subsequent to the index exacerbation) within the specified time period, for example, the 12-Week Treatment Period or the 24-Week Study Period.

The length of time on treatment or in study, depending on the specified time-period, for each participant will be calculated for each endpoint as follows:

Endpoint	Time period	Length of time derivation
Rate of (on-treatment) exacerbations, summarised by: 
 • Moderate/severe exacerbations • Moderate exacerbations • Severe exacerbations • All (mild, moderate and 	12-Week Treatment Period	Time from date of randomisation to date of last dose of study treatment

Endpoint	Time period	Length of time derivation
severe) exacerbations		
Rate of (on-or off-treatment) exacerbations, summarised by: 
 • Moderate/severe exacerbations • All exacerbations 	12-Week Treatment Period	Time from date of randomisation to Day 84 (Visit 6) Visit Date. For participants who withdraw early from the study: Time from date of randomisation to date of study withdrawal
Rate of (off-treatment) exacerbations, summarised by: 
 • Moderate/severe exacerbations • Moderate exacerbations • Severe exacerbations 	12-Week Follow Up Period	Time from date of last dose of study treatment to date of study withdrawal/completion
Rate of (on- and off- treatment) exacerbations, summarised by: 
 • Moderate/severe exacerbations • Moderate exacerbations • Severe exacerbations 	Full 24-Week Study Period	Time from date of randomisation to date of study withdrawal/completion

Refer to Section 13.5 for further details regarding the length of time derivation

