7.2.2. Time to next exacerbation

Time to next (on-treatment) exacerbation following index exacerbation during the 12-Week Treatment Period is defined as time from the date of randomisation until the date of onset of the first exacerbation whilst on study treatment. Participants who did not have an exacerbation whilst on study treatment will be censored at the date of their last dose of study treatment.

Time to next (on-or off-treatment) exacerbation during the 12-Week Treatment Period is defined as time from the date of randomisation until the date of onset of the first exacerbation occurring up to Day 84. Participants who have not had an exacerbation during the 12-Week Treatment Period will be censored at Day 84 or the date of study withdrawal, for participants who withdrew from the study prior to Day 84.

Time to next exacerbation following cessation of study treatment is defined as time from the date of last dose of study treatment until the date of onset of the next exacerbation whilst off study treatment during the 12-Week Follow Up Period. Participants who have not had an exacerbation off-treatment will be censored at the date of their last follow up assessment.

Time to next exacerbation will be analysed by severity, as follows:

Endpoint	Time period
Time to next (on-treatment) exacerbation, summarised by: 
 • Moderate/severe exacerbations • All (mild, moderate and severe) exacerbations 	12-Week Treatment Period
Time to next (on-or off-treatment) exacerbation, summarised by: 
 • Moderate/severe exacerbations • All exacerbations 	12-Week Treatment Period
Time to next exacerbation following cessation of treatment, summarised by: 
 • Moderate/severe exacerbations 	12-Week Follow Up Period

Refer to Section [13.5](#) for further details regarding the length of time derivation

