7.2.5.4. Statistical analyses

The proportion of participants achieving EXACT-defined recovery from the index exacerbation will be analysed using a Bayesian logistic regression model. Separate models will be fitted for each time-point.

Non-informative priors will be used for all modelling parameters. Wherever possible conjugate priors will be utilised.

The results of the analysis will be presented in terms of odds ratios together with its associated 95% HPD credible interval. The probability that the true odds ratio is greater than 1, in addition to other values appropriately selected based on the data, will be presented.

Time to EXACT-defined recovery from index exacerbation will be analysed using the same techniques as described in Section 7.2.2.1.

Severity of subsequent HCRU-defined exacerbation(s) defined by EXACT will be summarised for each treatment group and reported by study period. The severity of subsequent HCRU-defined exacerbation(s) occurring whilst a participant is on treatment will be reported as during the 12-Week Treatment Period and the severity of subsequent HCRU-defined exacerbation(s) occurring after the last dose of study treatment will be reported as during the 12-Week Follow-up Period.

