13.3.2. Study Phases

Exacerbation events during the 12-Week Treatment Period will be classified according to their occurrence from randomisation until treatment discontinuation/study withdrawal days, as detailed below.

Study Phase	Occurring from randomisation until
On-Treatment during the 12-Week Treatment Period	Treatment Stop Day
On- or Off-Treatment during the 12-Week Treatment Period	Day 84 or Study Withdrawal Day if Treatment Stop Day is < Day 84

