13.6. Appendix 6: Reporting Standards for Missing Data

13.6.1. Premature Withdrawals

Element	Reporting Detail
General	
 • Subject study completion (i.e. as specified in the protocol) is defined as completing all phases of the study including the last scheduled study visit • A participant is considered to have completed the Treatment Period, if he/she has completed the last on-treatment study visit (Visit 6) • Withdrawn subjects were not replaced in the study. • All available data from participants who were withdrawn from the study will be listed and all available planned data will be included in summary tables and figures, unless otherwise specified. • Withdrawal visits will not be summarised (and will be listed only).

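### For participants who stop treatment early, the SAP gives conflicting follow-up windows for exacerbation events and at-risk time; separately, the on-or-off-treatment rate ends events and exposure on different days

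*SAP*

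**What the plan says.** Section numbers refer to the current version of the SAP, the first in the file.

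**Follow-up window.** 13.3.1 sets both periods by study day: "The 12-Week Treatment Period is assigned from Study Day 1 to Study Day 84" and "The 12-Week Follow-up Period is assigned from Study Day 85 to Study Day 168". 7.2.1 defines a rate as the frequency of exacerbations within the stated period. It labels the off-treatment rate with the 12-Week Follow Up Period, but gives its length of time as "Time from date of last dose of study treatment to date of study withdrawal/completion". 13.5.1 reduces that to reference date minus last dose date, and 7.2.1.1 enters it as a log offset. In 7.2.2, time to exacerbation after cessation starts at the last dose and runs "until the date of onset of the next exacerbation whilst off study treatment during the 12-Week Follow Up Period".

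Two other sections tie follow-up to the last dose. For EXACT severity, 7.2.5.4 says that exacerbations "occurring after the last dose of study treatment will be reported as during the 12-Week Follow-up Period". For rescue medication, 7.2.8 starts Week 13, the first follow-up week, on the day after the last dose.

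**On-or-off-treatment rate.** 13.3.2 counts events from randomisation until "Day 84 or Study Withdrawal Day if Treatment Stop Day is < Day 84". 7.2.1 sets exposure as "Time from date of randomisation to Day 84 (Visit 6) Visit Date" and, for participants who withdraw early from the study, as time to the withdrawal date. The matching time-to-event endpoint in 7.2.2 censors at Day 84, or at withdrawal if that is before Day 84.

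**The concern.** A rate needs its events and its person-time to come from the same days. For someone who completes treatment the follow-up definitions agree. For someone who stops early they do not, and 13.3.2 does not settle the matter because it defines event phases for the Treatment Period only. Two programmers could follow this SAP and produce different off-treatment rates and hazard ratios.

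The parallel FEV₁ analysis avoids the problem: 7.3.1 excludes participants who discontinue before Day 84. The exacerbation endpoints have no such rule.

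The exploratory objective on post-treatment impact rests on these analyses. An arm with more early stoppers could show a small spurious benefit after cessation. The on-or-off-treatment rate is the version of the secondary exacerbation endpoint that keeps events after discontinuation, so its end date should be unambiguous. Tables 2.45, 2.48 and 2.50, which report the on-or-off-treatment and off-treatment rates, are also due at the End of Treatment Interim Analysis, which informs internal decisions (3.1).

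**Working it through.** **1. The plan's own figure.** Days 85 to 168 span 168 − 85 + 1 = 84 days = 12 weeks. For a last dose on Day 84, 13.5.1 gives 168 − 84 = 84 at-risk days. The windows agree for a completer.

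**2. One early stopper, literal reading, study completed on Day 168.** The offset is 168 − last dose day. Event days are Days 85-168.

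| Last dose | At-risk days | Event days | Fraction of true rate |
|---|---|---|---|
| Day 14 | 154 | 84 | 0.545 |
| Day 30 | 138 | 84 | 0.609 |
| Day 56 | 112 | 84 | 0.750 |
| Day 84 | 84 | 84 | 1.00 |

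The Day 30 stopper carries 84 − 30 = 54 days at risk on which no event can count.

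**3. Arm level.** The SAP gives no discontinuation rate. Assume a proportion q stops early, uniformly over Days 1-83 (mean Day 42, mean offset 168 − 42 = 126), with constant hazard and no drug effect. The fraction of the true rate is 84 / [84(1 − q) + 126q]:

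- q = 10%: 84/88.2 = 0.952
- q = 20%: 84/92.4 = 0.909
- q = 30%: 84/96.6 = 0.870

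The null rate ratio, active to placebo, is 1.00 when q is equal in both arms, 88.2/92.4 = 0.955 for 10% placebo v 20% active, and 88.2/96.6 = 0.913 for 10% v 30%.

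If follow-up instead ended 84 days after the last dose (assumption), the offset would be 84 days for everyone and the fraction would be 1 − 0.5q, that is 0.950, 0.900 and 0.850. The null ratios become 0.900/0.950 = 0.947 and 0.850/0.950 = 0.895.

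**4. Time after cessation.** Cox fits were simulated under no drug effect, with 20,000 per arm, an assumed 0.3 exacerbations per 12 weeks, and Breslow ties (the plan uses Efron). The standard error of the log hazard ratio was about 0.02.

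| Early stopping, placebo v active | HR, literal windows | HR, aligned windows |
|---|---|---|
| 10% v 10% | 1.01 | 1.01 |
| 10% v 20% | 0.95 | 1.00 |
| 10% v 30% | 0.89 | 1.03 |

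**5. What alignment to last dose leaves behind.** With events and time both counted from last dose, the null rate ratio is 1.00 under constant hazard. Early stoppers then contribute time nearer the index exacerbation. If the hazard before Day 85 were twice the later one (assumption), an average early stopper would contribute 42 × 2 + 84 = 168 hazard-weighted days over 126 at-risk days. The arm factors are:

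- q = 10%: (75.6 + 16.8)/88.2 = 92.4/88.2 = 1.048
- q = 20%: (67.2 + 33.6)/92.4 = 100.8/92.4 = 1.091
- q = 30%: (58.8 + 50.4)/96.6 = 109.2/96.6 = 1.130

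The null ratios are 1.091/1.048 = 1.04 and 1.130/1.048 = 1.08.

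**6. On-or-off-treatment rate.** Events and exposure both start at randomisation; only the ends differ.

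- Visit 6 date against Day 84: taking Days 80-87 as an assumed range (the Day 84 window in a superseded version of the SAP), 84/80 = 1.05 and 84/87 = 0.97.
- Withdrawal on Day 120 after completing treatment: events end at Day 84 (13.3.2), but the withdrawal sentence in 7.2.1 gives 120 days of exposure, so 84/120 = 0.70. Such a participant may also have a Visit 6 date, and 7.2.1 does not say which rule applies.
- The withdrawal clause in 13.3.2 depends on the treatment stop day and does not itself require withdrawal before Day 84. Only 7.2.2 says so.

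**The case against.** The strongest defence is that the literal Day 85-168 reading is not the one most of the SAP uses. The off-treatment rate and the time-after-cessation endpoint are named for, and timed from, the end of treatment. 7.2.5.4 and 7.2.8 place follow-up after the last dose, and the display titles for these analyses in 13.11.6.3 carry no Day 85-168 limit. A programmer who aligned events to the last dose would find no mismatch. This stands in part: the SAP contains an unresolved contradiction, not a settled wrong rule. It does not remove the point, because 7.2.1 and 7.2.2 still tie events to a period that 13.3.1.2 fixes by study day.

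Stakes are also limited. The follow-up endpoints are exploratory, on-treatment events and time are aligned, and futility uses FEV₁ and the on-treatment rate.

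Three stronger readings are tempting, and the document does not support them:

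- A reader might infer that these results reflect when people stop rather than what the drug does. Arm-level rates are biased low, but with equal stopping the null ratio is 1.00.
- A reader might infer that the on-or-off-treatment rate shares the follow-up mismatch. It does not use the Day 85-168 window; its fault is an inconsistent end date.
- A reader might infer that early stoppers who stay in the study have no Visit 6 date and hence no offset. 13.6.1 describes Visit 6 as an on-treatment visit only in defining completion of the Treatment Period. Whether discontinuers attend it is a protocol matter, and the protocol is not shown.

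**Conclusion.** The concern holds as a contradiction to be resolved. Under the literal reading, off-treatment rates fall to about 0.95, 0.91 and 0.87 of the truth with 10%, 20% and 30% early stoppers. Between-arm ratios shift by about 4-11% under assumed stopping of 10% v 20-30%, and do not shift if stopping is equal. These sizes rest on assumed stopping rates, uniform stop days and constant hazard.

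The on-or-off-treatment rate has a separate and smaller inconsistency. It amounts to a few days around Visit 6 for most participants, and more for anyone who withdraws from the study well after Day 84. The change should be made, but nothing here touches the primary endpoint, the on-treatment exacerbation analyses or the futility rules.

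**What to change.** (a) Add an off-treatment phase to 13.3.2, running from last dose + 1 to study withdrawal/completion. Use it for both events and time in the off-treatment rate (7.2.1) and the time-after-cessation analysis (7.2.2), with one end date in place of the two now used (withdrawal/completion in 7.2.1, last follow-up assessment in 7.2.2). State in 13.3.1.2 that the Day 85-168 label does not restrict these events. This matches 7.2.5.4. Note in the text that early stoppers then contribute time nearer the index exacerbation, and offer a common Day 85-168 window for events and time as an optional sensitivity analysis.

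A Day 85 start should not be the main definition. It would change the endpoint listed in 2.1, which is time from cessation. If carried into 7.2.5.4, it would leave the EXACT severity of exacerbations between last dose and Day 85 in neither reporting period.

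(b) For the on-or-off-treatment rate, end both events and exposure at min(Day 84, study withdrawal day) for every participant, in 7.2.1 and 13.3.2, as 7.2.2 already does.

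The cost is wording in 7.2.1, 7.2.2, 13.3.1.2 and 13.3.2 and a small derivation change. No new data are needed.

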13.3.2. Study Phases

Exacerbation events during the 12-Week Treatment Period will be classified according to their occurrence from randomisation until treatment discontinuation/study withdrawal days, as detailed below.

Study Phase	Occurring from randomisation until
On-Treatment during the 12-Week Treatment Period	Treatment Stop Day
On- or Off-Treatment during the 12-Week Treatment Period	Day 84 or Study Withdrawal Day if Treatment Stop Day is < Day 84

13.3.2.1. Study Phases for Concomitant Medication

Study Phase	Definition
Prior	If medication end date is not missing and is before Randomisation Date
Concomitant	Any medication that is not a prior

NOTES:

- Please refer to [Appendix 6: Reporting Standards for Missing Data](#) for handling of missing and partial dates for concomitant medication. Use the rules in this table if concomitant medication date is completely missing.

13.3.3. Treatment Emergent Flag for Adverse Events

Flag	Definition
Treatment Emergent	
 If AE onset date is on or after treatment start date & on or before treatment stop date plus 10 days.

NOTES:

- If the study treatment stop date is missing, then the AE will be considered to be On-Treatment.
- Time of study treatment dosing and start/stop time of AEs should be considered, if collected.

13.4. Appendix 4: Data Display Standards & Handling Conventions

13.4.1. Reporting Process

Software	

 The currently supported versions of SAS software will be used. 	
Reporting Area	
HARP Server	: uk1salx00175
HARP Compound	: \arprod\gsk2269557\mid200879
Analysis Datasets	

 For all interim analyses, except for the End of Treatment Interim Analysis, datasets will be created according to Legacy GSK A&R dataset standards. For the End of Treatment Interim Analysis and the final reporting effort, datasets will be created according to current CDISC standards 	
Generation of RTF Files	

 RTF files will be generated for the final reporting effort. 	

13.4.2. Reporting Standards

General	

 The current GSK Integrated Data Standards Library (IDSL) will be applied for reporting, unless otherwise stated (IDSL Standards Location: https://spope.gsk.com/sites/IDSLLibrary/SitePages/Home.aspx): 
 4.03 to 4.23: General Principles 5.01 to 5.08: Principles Related to Data Listings 6.01 to 6.11: Principles Related to Summary Tables 7.01 to 7.13: Principles Related to Graphics Figures will be produced using PROC SGPLOT in SAS 	
Formats	

 GSK IDSL Statistical Principles (5.03 & 6.06.3) for decimal places will be adopted for reporting of data based on the raw data collected, unless otherwise stated. Numeric data will be reported at the precision collected on the eCRF. The reported precision from non eCRF sources will follow the IDSL statistical principles but may be adjusted to a clinically interpretable number of decimal places. For lab parameters results that contain a character value of '<', or '>', e.g. '<X' or '>X', the parameter value will be imputed with X. 	
Planned and Actual Time	

 Reporting for tables, figures and formal statistical analyses: 
 Planned time relative to dosing will be used in figures, summaries, statistical analyses and calculation of any derived parameters, unless otherwise stated. The impact of any major deviation from the planned assessment times and/or scheduled visit days on the analyses and interpretation of the results will be assessed as appropriate. Reporting for Data Listings: 
 Planned and actual time relative to study drug dosing will be shown in listings (Refer to IDSL Statistical Principle 5.05.1). Unscheduled or unplanned readings will be presented within the subject's listings. 	

Unscheduled Visits	

 Unscheduled visits will be included in summary tables of the worst-case results by potential clinical importance criteria only. All unscheduled visits will be included in listings. 	
Descriptive Summary Statistics	
Continuous Data	Refer to IDSL Statistical Principle 6.06.1
Categorical Data	N, n, frequency, %
Graphical Displays	

 Refer to IDSL Statistical Principles 7.01 to 7.13. 	

13.4.3. Reporting Standards for Pharmacokinetic

Pharmacokinetic Concentration Data	
Descriptive Summary Statistics, Graphical Displays and Listings	Refer to IDSL PK Display Standards. Refer to IDSL Statistical Principle 6.06.1. Note: Concentration values will be imputed as per GUI_51487 for descriptive summary statistics/analysis and summarized graphical displays only.
NONMEM/Pop PK File	Pop-PK file (CSV format) for the POP-PK analysis by Clinical Pharmacology Modelling and Simulation function will be created according to the data specification detailed in Section 13.8.2 Population Pharmacokinetic (PopPK) Dataset Specification.
NONMEM/PK/PD File	PK/PD file (CSV format) for the PK/PD analysis by Clinical Pharmacology Modelling and Simulation function will be created according to the data specification detailed in the CPMS RAP.

13.5. Appendix 5: Derived and Transformed Data

13.5.1. General

Multiple Measurements at One Analysis Time Point

 Participants having both High and Low values for Normal Ranges at any post-baseline visit for safety parameters will be counted in both the High and Low categories of “Any visit post-baseline” row of related summary tables. This will also be applicable to relevant Potential Clinical Importance summary tables.
Study Day

 Calculated as the number of days from Randomisation Date: 
 Ref Date = Missing → Study Day = Missing Ref Date < Randomisation Date → Study Day = Ref Date – Randomisation Date Ref Date ≥ Randomisation Date → Study Day = Ref Date – (Randomisation Date) + 1
Time from date of randomisation and time from date of last dose of study treatment

 For endpoints that use the time from the date of randomisation to a reference date, time will be calculated as 
 (Ref Date – Randomisation Date) + 1 For endpoints that use the time from the date of last dose of study treatment to a reference date, time will be calculated as 
 (Ref Date – (Last Dose Date + 1)) + 1

13.5.2. Study Population

Extent of Exposure

 Number of days of exposure to study drug will be calculated based on the formula: Duration of Exposure in Days = Treatment Stop Date – (Treatment Start Date) + 1

13.5.3. Safety

Adverse Events
AE'S of Special Interest

 Post-inhalation cough: Lower level term (LLT) to be included is “coughing after drug inhalation” Paradoxical bronchospasm: Preferred Terms to be included are “Bronchospasm paradoxical” and “Bronchospasm”

13.6. Appendix 6: Reporting Standards for Missing Data

13.6.1. Premature Withdrawals

Element	Reporting Detail
General	
 • Subject study completion (i.e. as specified in the protocol) is defined as completing all phases of the study including the last scheduled study visit • A participant is considered to have completed the Treatment Period, if he/she has completed the last on-treatment study visit (Visit 6) • Withdrawn subjects were not replaced in the study. • All available data from participants who were withdrawn from the study will be listed and all available planned data will be included in summary tables and figures, unless otherwise specified. • Withdrawal visits will not be summarised (and will be listed only).

13.6.2. Handling of Missing Data

Element	Reporting Detail
General	
 • Missing data occurs when any requested data is not provided, leading to blank fields on the collection instrument: 
 • These data will be indicated by the use of a “blank” in subject listing displays. Unless all data for a specific visit are missing in which case the data is excluded from the table. • Answers such as “Not applicable” and “Not evaluable” are not considered to be missing data and should be displayed as such.
Outliers	
 • Any participants excluded from the summaries and/or statistical analyses will be documented along with the reason for exclusion in the clinical study report.

